Abbreviated Title: Pembrolizumab in MTC

CC Protocol #: 17-C-0061

Version Date: 3.26.18

NCT #: NCT03072160

Amendment: D

Title: Phase II Trial of Pembrolizumab in Recurrent or Metastatic Medullary Thyroid Cancer

NCI Principal Investigator: [name].
Genitourinary Malignancies Branch (GMB)
National Cancer Institute
[name]
[name]
[name]
[contact]
Email: [contact]

Commercial Agent: Pembrolizumab will be supplied by the manufacturer, Merck

PRÉCIS

Background:

- Anti PD1/PDL1 therapies have had clinical success in a minority of unselected patients across multiple tumor types
- While many questions remain about optimal PD1/PDL1 staining techniques to pre-select responders, less focus is being placed on how to optimize responses in a broader cohort of patients
- Emerging preclinical and clinical data supports the hypothesis that a strong immunologic response in the tumor microenvironment induces PDL1 expression on the tumor and is associated with better clinical response to anti-PD1/PDL1 therapies
- Therapeutic cancer vaccines are one strategy to induce an immunologic response to the tumor, thereby enhancing PDL1 expression and optimizing clinical responses across all patients
- Limited clinical data exists about the potential benefit of sequential therapy with a therapeutic cancer vaccine followed by PD1/PDL1 inhibition
- This study will explore the role of PD1 inhibition in medullary thyroid cancer and evaluate the potential differences based on previous vaccine therapy

Objective:

- The primary objective of this trial is to determine whether administering a PD1 inhibitor to patients with medullary thyroid cancer will permit a modest fraction to be able to experience a 50% or greater decline in calcitonin levels or experience a partial/complete response on imaging

Key Eligibility:

[figure not shown]
- Patients ≥ 18 years of age with evidence of metastatic medullary thyroid cancer including disease that is evaluable on bone, CT scan or MRI
- Must have elevated calcitonin levels greater than 40 pg/mL
- Patients with minimal or no disease related-symptoms (minimal symptoms will include those that do not affect activities of daily living or pain that does not require regularly schedule narcotics)
- ECOG 0-1
- Should have no autoimmune diseases; no evidence of being immunocompromised; no serious inter-current medical illness
- No brain metastasis, history of seizures, encephalitis, or multiple sclerosis

Design:

- This is a phase II, open label, single center clinical trial where all patients receive the anti-PD1/PDL1 therapy pembrolizumab

- Patients will enroll in one of two cohorts: patients with previous vaccine therapy or patients without previous vaccine therapy
- All patients will be TKI -naïve, with minimal symptoms (consistent with the eligibility for our current study)
- Based on our calcitonin findings with our current study of 30 patients, we have determined that a confirmed calcitonin decline of 50% would be a rare finding, providing compelling preliminary evidence of clinical activity
- A total of 30 patients will be enrolled in the proposed study (15 patients in each cohort). Given that we already have 30 patients on a study with vaccine, we would only need to identify and recruit 15 naïve patients for the vaccine-naïve cohort. This accrual could be done in 18 months based on our current accrual rates
- Based on these metrics, we could have >6 months of calcitonin data in 30 patients within 2 years from trial initiation
- Additional immune correlative capitalizing on the extensive immune monitoring experience of the LTIB will allow for assessments of antigen specific T-cells and 123 immune subsets. These findings could provide the basis for biomarker development when taken together with biochemical and clinical responses seen in this study

SCHEMA

Treatment Duration with Pembrolizumab: 2 years (at 3 week intervals)

TABLE OF CONTENTS

PRÉCIS.....	2
SCHEMA.....	3
TABLE OF CONTENTS.....	4
1 INTRODUCTION	8
1.1 Study Objectives	8
1.1.1 Primary Objectives.....	8
1.1.2 Secondary Objectives.....	8
1.2 Background and Rationale	8
1.2.1 Rationale for Dose Selection/Regimen/Modification.....	17
2 ELIGIBILITY ASSESSMENT AND ENROLLMENT.....	19
2.1 Eligibility Criteria	19
2.1.1 Inclusion Criteria	19
2.1.2 Exclusion Criteria	20
2.1.3 Recruitment Strategies	22
2.2 Registration Procedures.....	22
2.3 Screening Evaluation.....	23
2.3.1 The following tests may be obtained any time prior to initiation of study therapy:	23
2.3.2 The following parameters will be obtained within 8 weeks prior to initiation of study therapy:	23
2.3.3 The following parameters will be obtained within 10 days prior to initiation of study therapy:	23
2.4 Treatment Assignment and Randomization/Stratification Procedures:	24
2.5 Baseline Evaluation.....	24
3 STUDY IMPLEMENTATION	25
3.1 Study Design	25
3.2 Trial Treatments	25
3.3 Drug Administration	25
3.3.1 Dose Modifications.....	26

1 INTRODUCTION

1.1 Study Objectives

1.1.1 Primary Objectives

- Determine whether administering a PD1 inhibitor to patients with medullary thyroid cancer will permit a modest fraction to be able to experience a 50% or greater decline in calcitonin levels or experience partial/complete response on imaging. Based on our calcitonin findings with our current study of 30 patients, we have determined that a confirmed calcitonin decline of 50% would be a rare finding, providing compelling preliminary evidence of clinical activity.

1.1.2 Secondary Objectives

- Determine the impact of previous therapeutic cancer vaccine on response rates
- Evaluate immune responses in each cohort
- Evaluate changes in CEA and Calcitonin kinetics
- Evaluate impact on progression free survival and overall survival
- Evaluate the safety of anti-PD1/PDL1 therapy pembrolizumab

1.2 Background and Rationale

Background

Therapies targeting the PDL1/PD1 axis have become the primary focus of clinical immunotherapy development as a substantial amount of academic and industry resources are being used to develop these therapies. Several diseases have been noted for their impressive responses in individual patients (bladder cancer, lung cancer and melanoma) and emerging data suggest benefit across a broad range of tumors. Despite these impressive findings, regardless of tumor type, only a minority of patients have response to this therapy.¹ A lot of effort is being expended to develop a biomarker predicting response (such as PDL1 expression by the tumor) but techniques and standards remain elusive. A key focus of this study is to determine if therapeutic cancer vaccines can enhance responses to pembrolizumab, providing a proof of concept that sequential therapy with vaccine followed by checkpoint inhibition can optimize clinical and immunologic responses. If this hypothesis is correct, this study could define a technique substantially enhance the proportion of patients who respond the immune checkpoint inhibition with agents such as pembrolizumab.

Medullary Thyroid Cancer

Medullary thyroid cancer (MTC) is a neuroendocrine tumor of the parafollicular or C cells of the thyroid gland. MTC accounts for approximately 4% of thyroid carcinomas. Its estimated incidence in the United States for 2010 is about 1,300 to 2,200 patients. Sporadic MTC accounts for about 80% of all cases of the disease. The typical age of presentation is in the fifth

or sixth decade, and there may be a slight female preponderance.² Surgery is the only curative treatment for MTC and consists of total thyroidectomy with bilateral central lymphadenectomy.³

When there is no anatomic evidence of disease, despite detectable serum calcitonin or CEA, the best current option is observation.⁴ Therapeutic interventions at this stage of disease have not demonstrated clinical benefit. Empiric surgical procedures aimed to remove all the lymph nodes of the neck and the mediastinum have been proposed, but the results have largely been disappointing. These procedures may yield no tumor resection and are unlikely to provide a biochemical remission. Patients with rapidly progressive disease by anatomic imaging or biochemical doubling time < 2 years should be considered for treatment, ideally in the context of a well-designed clinical trial.⁵

Metastatic MTC is largely unresponsive to conventional cytotoxic chemotherapy and radiotherapy.⁶ Until recently, doxorubicin was the only US Food and Drug Administration (FDA)–approved treatment for patients with advanced thyroid cancer. Doxorubicin has resulted in transient tumor response rates in up to 20% of patients with MTC and is associated with significant toxicity.⁷

Promising results have been reported with vandetanib, an oral inhibitor of VEGFR, RET, and epidermal growth factor receptor (EGFR).^{8,9} An international randomized phase III trial of vandetanib (300 mg daily) was performed in patients with either sporadic or hereditary MTC. In a preliminary report of results (median follow-up 24 months), median progression-free survival was improved in patients randomly assigned to vandetanib versus placebo (hazard ratio 0.45, 95% CI 0.30 to 0.69).¹⁰ Based on these results, vandetanib was approved by the FDA in April 2011 for patients with late-stage (metastatic) MTC who are ineligible for surgery and who have disease that is growing or causing symptoms.¹¹ Its toxicity profile is extensive including diarrhea (56%), rash (45%) nausea (33%), hypertension (32%) headache (26%), fatigue (24%), decreased appetite (21%); Grade 3 toxicities include diarrhea (11%), hypertension (9%) and fatigue (6%). Therefore, toxicity limits its use in patients with small volume, asymptomatic or indolent disease.

Similarly cabozantinib has demonstrated improvement in PFS in a population of patients with advanced MTC (estimated median PFS was 11.2 months for cabozantinib versus 4.0 months for placebo (hazard ratio, 0.28; 95% CI, 0.19 to 0.40; P < .001) and is now FDA approved in MTC.¹² Unfortunately, toxicity was also significant with this treatment with common associated adverse events including diarrhea, palmar-plantar erythrodysesthesia, decreased weight and appetite, nausea, and fatigue. The impact of toxicity on the patients was clearly indicated based on the fact that 70% of patients required dose reductions and dosing delays in 65% of patients.

the tissue preserving inhibitory T-cell signaling through PD1/PDL1 and kill cancer cells. There is actually substantial evidence from colon cancer, that the presence of immune cells in resected samples is strongly associated with clinical outcomes, demonstrating the potential clinical impact of immune activity against cancer cells.¹⁵ Similar data is also emerging across many other tumor types.¹⁶ Taken a step further, cancer cells that can neutralize immune cells, perhaps with immune checkpoint inhibitors such as PDL1 have a greater likelihood of clonal propagation within a patient.

Figure 2: Effect of Vaccination on Tumor PD-L1 Expression

[figure not shown]

One study done in the LTIB (unpublished, [name] Lab) demonstrates that vaccine can indeed enhance tumor expression by tumor cells. These studies included a CEA-targeting vaccine and two cell line, MC38 (pictured) and Lewis Lung cancer

There is also growing data suggesting the mechanism by which immune cells in the tumor microenvironment may lead to increased PDL1 expression on tumor cells. Multiple studies have implicated $\text{INF-}\gamma$ as one mediator PDL1 expression by tumor cells. $\text{INF-}\gamma$ is a cytokine produced by activated T-cells, and thus biologically it would seem that it is a rational mechanistic trigger for PDL1 expression. Preclinical and clinical data supports this hypothesis.^{17,18} Preclinical studies evaluating established B16 tumors in C57BL/6, Balb/c mice demonstrated that vaccine combined with anti-PDL1 therapy had the greatest impact on tumor growth compared to vaccine or controls alone. Interestingly, that benefit was negated when an antibody binding to $\text{INF-}\gamma$ was introduced into the model, demonstrating its important role in the synergy of the two therapies. Also, interesting findings were noted when human tumors were evaluated for $\text{INF-}\gamma$. Tissue in melanoma patients that had increased genetic expression of genes consistent with $\text{INF-}\gamma$ production were associated with the greatest responses to anti-PD1 therapy.

[figure not shown]

The PD-1 receptor-ligand interaction is a major pathway hijacked by tumors to suppress immune control. The normal function of PD-1, expressed on the cell surface of activated T-cells under healthy conditions, is to down-modulate unwanted or excessive immune responses, including autoimmune reactions. PD-1 (encoded by the gene *Pdcd1*) is an Ig superfamily member related to CD28 and CTLA-4 which has been shown to negatively regulate antigen receptor signaling upon engagement of its ligands (PD-L1 and/or PD-L2). The structure of murine PD-1 has been resolved. PD-1 and family members are type I transmembrane glycoproteins containing an Ig Variable-type (V-type) domain responsible for ligand binding and a cytoplasmic tail which is responsible for the binding of signaling molecules. The cytoplasmic tail of PD-1 contains 2 tyrosine-based signaling motifs, an immunoreceptor tyrosine-based inhibition motif (ITIM) and an immunoreceptor tyrosine-based switch motif (ITSM). Following T-cell stimulation, PD-1 recruits the tyrosine phosphatases SHP-1 and SHP-2 to the ITSM motif within its cytoplasmic tail, leading to the dephosphorylation of effector molecules such as CD3 ζ , PKC θ and ZAP70

which are involved in the CD3 T-cell signaling cascade. The mechanism by which PD-1 down modulates T-cell responses is similar to, but distinct from that of CTLA-4 as both molecules regulate an overlapping set of signaling proteins. PD-1 was shown to be expressed on activated lymphocytes including peripheral CD4+ and CD8+ T-cells, B-cells, T regs and Natural Killer cells. Expression has also been shown during thymic development on CD4-CD8- (double negative) T-cells as well as subsets of macrophages and dendritic cells. The ligands for PD-1 (PD-L1 and PD-L2) are constitutively expressed or can be induced in a variety of cell types, including non-hematopoietic tissues as well as in various tumors. Both ligands are type I transmembrane receptors containing both IgV- and IgC-like domains in the extracellular region and contain short cytoplasmic regions with no known signaling motifs. Binding of either PD-1 ligand to PD-1 inhibits T-cell activation triggered through the T-cell receptor. PD-L1 is expressed at low levels on various non-hematopoietic tissues, most notably on vascular endothelium, whereas PD-L2 protein is only detectably expressed on antigen-presenting cells found in lymphoid tissue or chronic inflammatory environments. PD-L2 is thought to control immune T-cell activation in lymphoid organs, whereas PD-L1 serves to dampen unwarranted T-cell function in peripheral tissues. Although healthy organs express little (if any) PD-L1, a variety of cancers were demonstrated to express abundant levels of this T-cell inhibitor. PD-1 has been suggested to regulate tumor-specific T-cell expansion in subjects with melanoma (MEL). This suggests that the PD-1/PD-L1 pathway plays a critical role in tumor immune evasion and should be considered as an attractive target for therapeutic intervention.

Pembrolizumab is a potent and highly selective humanized monoclonal antibody (mAb) of the IgG4/kappa isotype designed to directly block the interaction between PD-1 and its ligands, PD-L1 and PD-L2. Pembrolizumab™ (pembrolizumab) has recently been approved in the United States for the treatment of patients with unresectable or metastatic melanoma and disease progression following ipilimumab and, if BRAF V600 mutation positive, a BRAF inhibitor.

1.2.1 Rationale for Dose Selection/Regimen/Modification

An open-label Phase I trial (Protocol 001) is being conducted to evaluate the safety and clinical activity of single agent pembrolizumab (MK-3475). The dose escalation portion of this trial evaluated three dose levels, 1 mg/kg, 3 mg/kg, and 10 mg/kg, administered every 2 weeks (Q2W) in subjects with advanced solid tumors. All three dose levels were well tolerated and no dose-limiting toxicities were observed. This first in human study of pembrolizumab (MK-3475) showed evidence of target engagement and objective evidence of tumor size reduction at all dose levels (1 mg/kg, 3 mg/kg and 10 mg/kg Q2W). No MTD has been identified to date. 10.0 mg/kg Q2W, the highest dose tested in PN001, will be the dose and schedule utilized in Cohorts A, B, C and D of this protocol to test for initial tumor activity. Recent data from other clinical studies within the pembrolizumab (MK-3475) program has shown that a lower dose of pembrolizumab (MK-3475) and a less frequent schedule may be sufficient for target engagement and clinical activity.

PK data analysis of pembrolizumab (MK-3475) administered Q2W and Q3W showed slow systemic clearance, limited volume of distribution, and a long half-life (refer to IB).

Pharmacodynamic data (IL-2 release assay) suggested that peripheral target engagement is durable (>21 days). This early PK and pharmacodynamic data provides scientific rationale for testing a Q2W and Q3W dosing schedule.

A population pharmacokinetic analysis has been performed using serum concentration time data from 476 patients. Within the resulting population PK model, clearance and volume parameters of pembrolizumab (MK-3475) were found to be dependent on body weight. The relationship between clearance and body weight, with an allometric exponent of 0.59, is within the range observed for other antibodies and would support both body weight normalized dosing or a fixed dose across all body weights. Pembrolizumab (MK-3475) has been found to have a wide therapeutic range based on the melanoma indication. The differences in exposure for a 200 mg fixed dose regimen relative to a 2 mg/kg Q3W body weight based regimen are anticipated to remain well within the established exposure margins of 0.5 – 5.0 for pembrolizumab (MK-3475) in the melanoma indication. The exposure margins are based on the notion of similar efficacy and safety in melanoma at 10 mg/kg Q3W vs. the proposed dose regimen of 2 mg/kg Q3W (i.e. 5-fold higher dose and exposure). The population PK evaluation revealed that there was no significant impact of tumor burden on exposure. In addition, exposure was similar between the NSCLC and melanoma indications. Therefore, there are no anticipated changes in exposure between different indication settings.

The rationale for further exploration of 2 mg/kg and comparable doses of pembrolizumab in solid tumors is based on: 1) similar efficacy and safety of pembrolizumab when dosed at either 2 mg/kg or 10 mg/kg Q3W in melanoma patients²⁰ 2) the flat exposure-response relationships of pembrolizumab for both efficacy and safety in the dose ranges of 2 mg/kg Q3W to 10 mg/kg Q3W, 3) the lack of effect of tumor burden or indication on distribution behavior of pembrolizumab (as assessed by the population PK model) and 4) the assumption that the dynamics of pembrolizumab target engagement will not vary meaningfully with tumor type.

The choice of the 200 mg Q3W as an appropriate dose for the switch to fixed dosing is based on simulations performed using the population PK model of pembrolizumab showing that the fixed dose of 200 mg every 3 weeks will provide exposures that 1) are optimally consistent with those obtained with the 2 mg/kg dose every 3 weeks, 2) will maintain individual patient exposures in the exposure range established in melanoma as associated with maximal efficacy response and 3) will maintain individual patients exposure in the exposure range established in melanoma that are well tolerated and safe.

A fixed dose regimen will simplify the dosing regimen to be more convenient for physicians and to reduce potential for dosing errors. A fixed dosing scheme will also reduce complexity in the logistical chain at treatment facilities and reduce wastage.

2 ELIGIBILITY ASSESSMENT AND ENROLLMENT

2.1 Eligibility Criteria

2.1.1 Inclusion Criteria

- 2.1.1.1 Diagnosis: Patients must have histologically confirmed medullary thyroid cancer by the Laboratory of Pathology or a pathology report and history consistent with medullary thyroid cancer. It is not uncommon for a secondary, minor pathologic focus of another form of thyroid cancer to be coincidentally found in 15-20% of patients with medullary thyroid cancer²¹. In such cases, eligibility is based on the discretion of the investigator.
- 2.1.1.2 Patients must have evidence of metastatic medullary thyroid cancer including disease that is evaluable on bone, CT scan or MRI. (Patients who are surgical candidates and potentially rendered disease free with surgical resection are not eligible.)
- 2.1.1.3 Patients must have elevated calcitonin levels greater than 40 pg/mL
- 2.1.1.4 Patients must have minimal or no disease related-symptoms (Minimal symptoms will include those that do not affect activities of daily living or pain that does not require regularly scheduled narcotics.)
- 2.1.1.5 Patients must have evaluable disease on imaging
- 2.1.1.6 No history of seizures, encephalitis, or multiple sclerosis.
- 2.1.1.7 Age \geq 18 years
- 2.1.1.8 ECOG performance status of 0-1 at study entry (Karnofsky \geq 70) (See [Appendix A](#)).
- 2.1.1.9 Female subject of childbearing potential should have a negative urine or serum pregnancy within 72 hours prior to receiving the first dose of study medication. If the urine test is positive or cannot be confirmed as negative, a serum pregnancy test will be required.
- 2.1.1.10 Female subjects of childbearing potential must be willing to use an adequate method of contraception as outlined in Section [10.6](#), Contraception, for the course of the study through 120 days after the last dose of study medication.
Note: Abstinence is acceptable if this is the usual lifestyle and preferred contraception for the subject
- 2.1.1.11 Male subjects of childbearing potential must agree to use an adequate method of contraception as outlined in Section [10.6](#), Contraception, starting with the first dose of study therapy through 120 days after the last dose of study therapy.
Note: Abstinence is acceptable if this is the usual lifestyle and preferred contraception for the subject
- 2.1.1.12 Willing to travel to the NIH for follow-up visits
- 2.1.1.13 Able to understand and sign informed consent.
- 2.1.1.14 Demonstrate adequate organ function as defined in [Table 2](#), all screening labs should be performed within 10 days of treatment initiation.

Table 2 Adequate Organ Function Laboratory Values

System	Laboratory Value
Hematological	
Absolute neutrophil count (ANC)	$\geq 1,000$ /mcL
Platelets	$\geq 100,000$ / mcL
Hemoglobin	≥ 9 g/dL or ≥ 5.6 mmol/L without transfusion or EPO dependency (within 7 days of assessment)
Renal	
Serum creatinine OR Measured or calculated ^a creatinine clearance (GFR can also be used in place of creatinine or CrCl)	≤ 1.5 X upper limit of normal (ULN) OR ≥ 60 mL/min for subject with creatinine levels > 1.5 X institutional ULN
Hepatic	
Serum total bilirubin	≤ 1.5 X ULN OR Direct bilirubin \leq ULN for subjects with total bilirubin levels > 1.5 ULN
AST (SGOT) and ALT (SGPT)	≤ 2.5 X ULN OR ≤ 5 X ULN for subjects with liver metastases
Albumin	≥ 2.5 mg/dL
Coagulation	
International Normalized Ratio (INR) or Prothrombin Time (PT)	≤ 1.5 X ULN unless subject is receiving anticoagulant therapy as long as PT or PTT is within therapeutic range of intended use of anticoagulants
Activated Partial Thromboplastin Time (aPTT)	≤ 1.5 X ULN unless subject is receiving anticoagulant therapy as long as PT or PTT is within therapeutic range of intended use of anticoagulants
^a Creatinine clearance should be calculated per Cockcroft-Gault equation.	

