2.3.3.2 Laboratory studies

- Complete blood count plus differential and platelet count
- Chemistries (sodium, potassium, chloride, CO₂, creatinine, glucose, BUN, albumin, calcium, magnesium, phosphorus, alk phos, ALT, AST, total bilirubin, direct bilirubin, LD, total protein, total CK and uric acid)
- PT, PTT
- Urinalysis (may be omitted if patient is incontinent and cannot provide a urine sample)
- Serum calcitonin and CEA
- TSH
- Urine Beta-HCG for women of child-bearing age (repeated within 48 hours prior to treatment). (Serum Beta-HCG may be done if urine is positive or inconclusive).

Females of childbearing potential (FCBP): A female of childbearing potential is a sexually mature woman who:

- a) Has not undergone a hysterectomy or bilateral oophorectomy
- b) Has not been naturally postmenopausal for at least 24 consecutive months (i.e. has had menses at any time in the preceding 24 consecutive months).
- c) Has a congenital or acquired condition that prevents childbearing

In addition, patients, both male and female, should be willing to practice effective birth control during the study and for four months following the last study treatment, unless they have had a prior hysterectomy, bilateral oophorectomy, congenital conditions associated with infertility or azoospermia.

2.4 Treatment Assignment and Randomization/Stratification Procedures:

Cohorts

Number	Name	Description
1	First cohort	Patients with prior vaccine therapy
2	Second cohort	Patients without prior vaccine therapy

Arms

Number	Name	Description
1	Pembrolizumab	Pembrolizumab treatment for 2 years at Q3W

Randomization and Arm Assignment

Patients will be enrolled to Cohort 1 (previous vaccine) or Cohort 2 (no previous vaccine) based on their treatment history. This will be established at each patients' screening visit and noted on the eligibility criteria. Patients in cohort 1 and cohort 2 will be directly assigned to Arm 1.

[figure not shown]

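### The albumin limit in Table 2 is printed in mg/dL, so that one row excludes nobody as written; the unit looks like a slip and should be confirmed (minor)

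*Combined protocol and SAP*

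**What the plan says.** Section 2.1.1.14 is an inclusion criterion. Patients must "Demonstrate adequate organ function as defined in" Table 2, and the same item adds that "all screening labs should be performed within 10 days of treatment initiation". The hepatic block of Table 2 has three rows:

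- total bilirubin, as a multiple of the upper limit of normal, with a direct-bilirubin alternative ("ULN for subjects with total bilirubin levels > 1.5 ULN");
- AST and ALT: "≤ 2.5 X ULN OR ≤ 5 X ULN for subjects with liver metastases";
- albumin: "Albumin ≥ 2.5 mg/dL".

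The hemoglobin row of the same table is given on the g/dL scale, with a second unit beside it: "≥ 9 g/dL or ≥ 5.6 mmol/L without transfusion or EPO dependency".

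Albumin is measured at screening. Section 2.3.3.2 lists it among the chemistries ("creatinine, glucose, BUN, albumin, calcium, magnesium, phosphorus"), and it appears again in footnote 7 of the Study Calendar and in Appendix B. None of these places gives a unit or a limit, so Table 2 is the only statement of the albumin criterion.

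**The concern.** Serum albumin is a quantity on the g/dL scale. A limit of 2.5 on the mg/dL scale lies far below any value a patient could have, so a criterion that should act as an objective screen cannot act.

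Table 2 is operative text. Under section 2.2, a completed eligibility checklist goes to the Central Registration Office before a patient is registered for treatment. A numeric criterion there should be usable as printed.

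The unit also decides what counts as a departure from protocol. Suppose a patient enters with an albumin of 1.5 g/dL. Under the printed text this row is met. If the same number were meant in g/dL, the row is failed and the enrollment is a protocol deviation as defined in section 7.1.8, reportable within 7 days under section 7.2.1.

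**Working it through.** **The plan's own figures.** The albumin limit has no derivation to reproduce. The calculated probabilities in section 8 come from the rule of 4 or more responders among 15 patients, and were checked with the exact binomial tail, 1 − Σ(k = 0 to 3) C(15, k) p^k (1 − p)^(15 − k):

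- p = 0.10: 0.0556, stated as 5.6%;
- p = 0.40: 0.9095, stated as 90.9%.

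Both reproduce, and albumin enters neither.

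**Inputs for the unit check.**

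- Printed limit: 2.5 mg/dL (Table 2).
- Conversion: 1 g/dL = 1,000 mg/dL.
- Serum albumin range: 1.0 to 5.5 g/dL. This is an assumption, since the documents give none; it is wide on purpose and extends to severe hypoalbuminemia.

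**Step 1, the limit in g/dL.** 2.5 / 1,000 = 0.0025 g/dL.

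**Step 2, patient values against the printed limit.** Ratio = (albumin in g/dL × 1,000) / 2.5.

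| Albumin, g/dL | mg/dL | Multiple of printed limit | Row met? |
|---|---|---|---|
| 1.0 | 1,000 | 400 | yes |
| 1.5 | 1,500 | 600 | yes |
| 2.5 | 2,500 | 1,000 | yes |
| 3.5 | 3,500 | 1,400 | yes |
| 5.5 | 5,500 | 2,200 | yes |

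The result is not sensitive to the assumed range. To fail the row, a patient would need an albumin 400 times lower than the bottom of it.

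**Step 3, the likely source.** If the same number were read in g/dL, the limit would be 2,500 mg/dL, exactly 1,000 times the printed one. It would then fall inside the assumed range, and values from 1.0 up to just under 2.5 g/dL would fail. This shows only that a slip of mg for g would explain the entry. It does not establish which limit was intended.

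**Step 4, the other rows.** The bilirubin and AST/ALT limits are multiples of the upper limit of normal. They do not depend on the albumin unit and can exclude patients as written.

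**The case against.** The strongest reply is that this is a one-letter slip with no shown effect. Staff would probably read the limit as g/dL, in which case the row works and the mismatch is formal. The trial is single-center, so different readings at different sites are not at issue. Patients must have minimal or no symptoms and ECOG 0–1, so few, perhaps none, would have a very low albumin. All of this stands, and it is why the point is minor. It does not make the printed limit usable.

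A reader might also infer more than the documents support:

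- **That the hepatic-function criterion as a whole excludes nobody.** It does not follow. Two of the three hepatic rows have workable limits.
- **That a patient with severe hypoalbuminemia is therefore eligible.** Passing one row is not eligibility. Exclusion 2.1.2.11 lets the investigator exclude for a laboratory abnormality, and 2.1.2.19 covers serious intercurrent illness. These rest on judgment and do not replace a numeric limit, but they can still keep such a patient out.
- **That the treated population differs from the one intended.** That would need an enrolled patient below the intended limit. The documents contain no enrollment or albumin data, and the intended limit is not stated.

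The unit might also have been altered when the PDF was read. This is unlikely, because mg/dL is a valid unit and hemoglobin in the same table appears in g/dL, but it cannot be fully ruled out from the text. The sponsor can settle it by looking at the source page.

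**Conclusion.** The point holds for the albumin row alone. As printed, its limit is 0.0025 g/dL and every patient meets it, on the assumption that serum albumin lies between 1.0 and 5.5 g/dL. That the cause is mg written for g is an inference from the scale of the analyte and from the hemoglobin row; the documents do not state the intended unit.

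Nothing in the inference changes. The primary endpoint, the two cohorts of 15, the threshold of 4 responders and the 5.6% and 90.9% probabilities are untouched. The number of patients affected is unknown and may be zero. This is a minor unit correction in an eligibility table.

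**What to change.** 1. The sponsor confirms the intended albumin limit and its unit. This review does not propose a value.
2. The single Table 2 cell is corrected at the next amendment, on the scale the laboratory reports, and the eligibility checklist is made to match.
3. Once the limit is confirmed, and not before, screening albumin values already collected can be checked against it. With an accrual ceiling of 32, this is one value for each of at most 32 patients.

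The cost is one table cell, one checklist line and a short look-back. Albumin is already in the screening chemistries, so no test or visit is added, and section 8 needs no change.
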